Based on limited response to primary therapy, many will go on to require additional immune suppressive agents for chronic GVHD control. Steroid-refractory chronic GVHD has most commonly been defined as either progressive manifestations despite one month, or rather incomplete response despite two months of 1-2mg/kg of prednisone or equivalent.² Multiple immune suppressive agents, including pharmacologic agents, monoclonal antibodies, and strategies such as extracorporeal photopheresis have demonstrated moderate activity in this setting, both ameliorating objective chronic GVHD manifestations, as well as importantly facilitating liberation from systemic steroids. Their activity is incomplete, however, and many with steroid-refractory chronic GVHD will require multiple agents to achieve disease control. The overall burden of chronic GVHD despite routine pharmacologic GVHD prophylaxis, limited response to

primary and salvage therapy, and the attendant morbidity and mortality all speak to the rationale for novel approaches to primary therapy.

Assessment of therapeutic response in chronic GVHD

The established method for response determination in the majority of chronic GVHD therapy trials is that of clinician-determined response. This method relies on the treating clinician's integration of dynamic chronic GVHD manifestations for a summary response categorization of complete response (CR), partial response (PR), stable disease (SD), or progressive disease (PD). CR indicates complete resolution of all chronic GVHD manifestations; PR signifies reduction in disease activity at response assessment compared to pre-treatment levels, but without complete resolution; SD indicates no response and no progression; and PD indicates progressive chronic GVHD manifestations from baseline to response assessment. This response assessment tool will be utilized for the primary endpoint of 6 month ORR in this trial, and for the purpose of power/sample size estimation with reference to historical published data on 6 month ORR according to this metric.

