Chronic GVHD is a major source of morbidity, mortality, and impaired quality of life after HCT. Despite prophylactic immune suppressive agents delivered prior to and following HCT, the majority of patients will develop chronic GVHD. The currently accepted primary therapy of chronic GVHD, namely 1mg/kg or greater of prednisone or equivalent, is ineffective, and available immune suppressive agents have limited activity in those who fail primary therapy. These all speak to the need for more effective primary therapy for chronic GVHD. Based on compelling clinical and basic insights into chronic GVHD biology, anti-CD20 based therapy has great potential to improve the success of chronic GVHD therapy. Thus, we propose a phase I-II study of combined ofatumumab and standard glucocorticoids to study the safety and efficacy of this approach.

II. STUDY OBJECTIVES

Primary Objectives:

1. Phase I: Determine the safety of ofatumumab in combination with steroids in the primary therapy of chronic GVHD
2. Phase II: Determine overall response rate (CR+PR) at 6 months to ofatumumab and glucocorticoid primary therapy of chronic GVHD.

Secondary Objectives:

1. Determine 6 month complete response rate to ofatumumab and steroids in the primary therapy of chronic GVHD.
2. Examine cumulative incidence of non-relapse mortality and primary disease relapse, and estimate overall survival from time of therapy.
3. Report utilization of second-line immune suppressive therapies.
4. Examine incidence of complete discontinuation of immune suppressive therapy .
5. Determine failure-free survival (composite outcome of death, relapse and requirement for secondary immune suppressive agents) and treatment success (composite outcome defined as complete resolution of all reversible chronic GVHD manifestations, discontinuation of all systemic immune suppressive agents, and freedom from death or primary malignancy relapse).
6. Evaluate serial measures of patient-reported outcomes following therapy, including functional ability, symptom burden, and quality of life.
7. Perform allied biologic studies for total B cells, B cell subsets, immune globulin levels, BAFF levels, and examine association between these biologic endpoints and clinical response to primary therapy.

III. STUDY DESIGN AND ENROLLMENT CRITERIA

Summary of Trial design

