- vi. Plan for patients not able to be evaluated for outcome on phase I component:
 1. If an enrolled patient dies or comes off study following occurrence of DLT as defined above, this data will inform the

determination of DLT, and there will be no need to replace such patients.

2. Rather, if an enrolled patient does not experience DLT during follow up, but decides to withdraw from the study for other non-DLT related reasons prior to the minimum follow up of 46 days, such a patient would be replaced by a newly accrued patient.

2. Efficacy

a. Overall response rate

- i. Overall response rate (ORR) at 6 months following initiation of therapy represents the composite outcome of complete and partial response (CR + PR).
- ii. Complete response is defined as resolution of all reversible manifestations in each organ or site of chronic GVHD involvement
- iii. Partial response is defined as improvement in at least one organ or site without progression in any other organ or site

b. Complete response rate

- i. Complete response (CR) at 6 months following initiation of therapy requires complete resolution of all chronic GVHD manifestations in all affected organs.

c. Cumulative incidence of non-relapse mortality and primary malignancy relapse

- i. The cumulative incidence of non-relapse mortality (defined as death in the absence of primary malignancy relapse after transplant) and relapse (defined by usual definitions in clinical practice including, but not limited to morphologic, immunophenotypic, or molecular methods) will be estimated from time of study therapy initiation. These are treated as competing-risk events.

d. Overall survival

- i. Overall survival will be determined from date of study therapy initiation, with death from any cause as the event of interest, and censoring at last follow up date for those with incomplete observations.

e. Utilization of second-line systemic immune suppressive therapies

- i. The use of second-line systemic immune suppressive agents will be captured at each study visit.
- ii. This specifically refers to systemic therapies only, not topical or local therapies, such as topical eye drops, mouth rinses, topical steroid skin cream, or topical vaginal steroid agents.

- iii. Adjustment in prednisone dose according to disease manifestations is not considered second-line therapy

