 - iv. Adjustment in the dose of existing immune suppressive agents that require dose modification to maintain therapeutic serum drug levels (e.g. tacrolimus, cyclosporine, sirolimus) is not considered a second-line therapy or change in therapy
 - v. New initiation of extra-corporeal photopheresis (ECP) for progressive chronic GVHD manifestations following study intervention of prednisone and ofatumumab is considered second-line therapy.
- f. Discontinuation of all systemic immune suppressive therapies
- i. The incidence of complete discontinuation of all systemic immune suppressive therapies will be determined.
- g. Failure-free survival
- i. This time-to-event outcome will be estimated with the composite event of death from any cause, relapse and addition of secondary immune suppressive agents for progressive chronic GVHD.
- h. Treatment success
- i. This endpoint will be estimated with a composite outcome of complete resolution of all reversible chronic GVHD manifestations, discontinuation of all systemic immune suppressive agents, and freedom from death or primary malignancy relapse after transplant.
- i. Patient-reported outcomes and functional measures
- i. Patients will provide assessment of their functional ability (grip strength, 2 minute walk test), symptom burden (Lee symptom scale), and quality of life using validated instruments recommended by the NIH Consensus Development Project on Chronic GVHD (Lee Chronic GVHD Symptom Scale,⁴¹ HAP functional scale,⁴² QOL instruments SF-36⁴³ and FACT-BMT⁴⁴)
 - ii. These data will be collected at baseline, 3, 6, and 12 months on study
- j. Biologic studies

Peripheral blood samples will be obtained from study patients at baseline, and then 3, 6, and 12 months. From these peripheral blood samples, the following major analyses will be performed: (1) quantification of plasma B cell stimulatory factor (BAFF), (2) quantification of immune globulin levels, and (3) enumeration of total B cells, as well as characterization of B cell subsets by surface phenotype through flow cytometric analysis.

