Following definition of the maximal tolerated dose (MTD) in the phase I component, this MTD will be taken forward in a phase II trial to characterize the efficacy of this approach. The primary endpoint of interest in the phase II component is overall response rate (ORR) to therapy at 6 months. Overall response is defined as the composite of complete response and partial response. In the assessment of response for this primary endpoint, response will be determined according to clinician assessment. The Simon's two-stage optimum design is used to minimize the expected sample size. With a historical baseline ORR proportion of 60% (*justification for this baseline proportion in background section*), anticipated effect leading to ORR of 80% in this investigational treatment (prednisone + ofatumumab), power of 90%, and alpha of 0.1, a total of 38 subjects are needed for this analysis of efficacy. As 6 total patients from the phase I component will have been treated at the recommended phase II dose, these will be included for efficacy analysis. Early termination will occur if 6 or fewer out of 11 ($\leq 6/11$) subjects in first stage have a overall response (CR or PR). If the trial goes on the second stage and a total number of responders (CR or PR) is less than or equal to 26 ($\leq 26/38$), the null hypothesis fails to be rejected. To provide total of 38 subjects for this efficacy analysis, 32 additional patients will be enrolled in the phase II component. Thus, the net total number of patients to be enrolled on the combined phase I-II study will be a maximum of 50.

Statistical Analysis plan:

The 'All Treated population' will be used for the analysis of the efficacy and safety endpoints. Specifically, this will consist of all patients who receive at least one dose of study treatment. For Complete Response (CR) rate and Overall Response rate: A

patient with unknown or missing response will be treated as a non-responder (i.e. the patient will be included in the denominator when calculating the percentage).

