Overall response (ORR) rate will be determined at 6 months and will be reported with associated 95% confidence interval. Complete response rate will be similarly reported. Association between clinical variables (chronic GVHD severity, organ involvement, patient socio-demographic data, disease and transplantation variables) and response will be examined. Patient reported outcomes will be reported, and association between scores on individual measures (chronic GVHD symptom scale, human activity profile, QOL instruments including SF-36 and FACT-BMT) and clinical response to therapy will be explored. Cumulative incidence of relapse and non-relapse mortality will be estimated, accounting for competing risk events. Overall survival from date of therapy initiation will be estimated by Kaplan-Meier method, and survival curves among relevant subgroups will be compared utilizing the log-rank test. In the analysis of survival time between responders and non-responders, landmark analysis will be utilized to avoid biased survival estimation. Other time-to-event secondary endpoints (e.g. failure-free survival) will similarly be estimated using the Kaplan-Meier method. Biologic endpoints (total B cell numbers, B cell subsets, immune globulin levels, BAFF levels) will be summarized. Comparisons between relevant groups will be made at specific time points utilizing parametric (e.g. t-test) or non-parametric (e.g. Wilcoxon rank-sum) as appropriate per the nature of the data. Additionally, change in these values over time will be examined according to response vs. non-response to primary therapy with mixed-model approach.

Early Stopping Rule for Toxicity

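### The primary 6-month ORR has no rule for second-line systemic therapy, so read literally a CR/PR reached after salvage for progression counts as a response to the study regimen

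*Combined protocol and SAP*

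**What the plan says.** The phase II primary objective (section II) is tied to the regimen: "Determine overall response rate (CR+PR) at 6 months to ofatumumab and glucocorticoid primary therapy of chronic GVHD". The Statistical Analysis plan in section VI uses the same idea for the biologic endpoints: "change in these values over time will be examined according to response vs. non-response to primary therapy".

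The counting rules do not mention added therapy:

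- V.2.a, endpoint: "Overall response rate (ORR) at 6 months following initiation of therapy represents the composite outcome of complete and partial response (CR + PR").
- V.2.a, PR: "Partial response is defined as improvement in at least one organ or site without progression in any other organ or site". CR is likewise defined by organ state.
- Background, on assessment of therapeutic response: "PR signifies reduction in disease activity at response assessment compared to pre-treatment levels, but without complete resolution".
- Section VI, the only stated rule that turns a patient into a non-responder: a "patient with unknown or missing response will be treated as a non-responder".

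Second-line therapy is handled elsewhere. V.2.e makes its use a separate endpoint, with exclusions for topical agents, prednisone dose changes and level-guided dose changes of existing agents, and with one explicit inclusion: "New initiation of extra-corporeal photopheresis (ECP) for progressive chronic GVHD manifestations following study intervention of prednisone and ofatumumab is considered second-line therapy". V.2.g makes it part of failure-free survival, the "composite event of death from any cause, relapse and addition of secondary immune suppressive agents for progressive chronic GVHD". It is not among the criteria for termination from study in V.4, and the Study Calendar keeps response assessment at month 6 for everyone still on study.

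**The concern.** Consider a patient who progresses after ofatumumab and prednisone, starts photopheresis, and at month 6 is better than before treatment in one organ with no organ worse. By V.2.a this is a PR and counts towards the primary endpoint. By V.2.g the same patient has already failed. The stated objective points to the second view, but no scoring rule carries it into ORR.

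The situation is foreseeable. The Background says that many patients need additional agents after primary therapy and that those agents have moderate activity, and reporting second-line use is itself a secondary objective.

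At stake is the phase II decision. It is a single-arm comparison with a fixed 60%, decided by responder counts at 11 and 38 patients. One patient is 1/38 = 2.6 percentage points. A response that occurs only because of another agent would be credited to ofatumumab plus prednisone in those counts.

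**Working it through.** **Inputs from section VI, phase II component.** Null ORR 60%, target 80%, alpha 0.10, power 90%. Stop if 6 or fewer of 11 respond; the null is not rejected if 26 or fewer of 38 respond.

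**Step 1: reproduce the design.** The probability of rejecting the null at a counted response rate p is

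R(p) = Σ (x = 7 to 11) C(11,x) pˣ (1−p)¹¹⁻ˣ × P[Bin(27, p) ≥ 27 − x].

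At p = 0.60 the five terms are 0.0225 + 0.0326 + 0.0274 + 0.0122 + 0.0022 = 0.0970 (to rounding). At p = 0.80, R = 0.9042. A search over two-stage designs gives 6/11 and 26/38 as the optimal design, so the plan's own figures are confirmed.

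**Step 2: set up the two scorings.** Let p be the response rate due to the study regimen, t the share of all patients in CR/PR at month 6 after starting second-line therapy, and f the fraction of those whose response is due only to the added agent.

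- Literal scoring (counts them): rate p + f·t.
- Strict scoring (non-responders): rate p − (1 − f)·t.

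A strict responder is always a literal responder, so the probability that the verdicts differ is R(literal) − R(strict). Neither t nor f is in the documents. Here t = 0.05 is assumed and f runs over its whole range.

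| Regimen response | f | R literal | R strict | Verdicts differ |
|---|---|---|---|---|
| 60% | 1 | R(0.65) = 0.2474 | R(0.60) = 0.0970 | 15.0% |
| 60% | 0.5 | R(0.625) = 0.1604 | R(0.575) = 0.0545 | 10.6% |
| 60% | 0 | R(0.60) = 0.0970 | R(0.55) = 0.0284 | 6.9% |
| 80% | 1 | R(0.85) = 0.9783 | R(0.80) = 0.9042 | 7.4% |
| 80% | 0.5 | R(0.825) = 0.9517 | R(0.775) = 0.8305 | 12.1% |
| 80% | 0 | R(0.80) = 0.9042 | R(0.75) = 0.7303 | 17.4% |

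Neither scoring is right throughout. Literal scoring matches the regimen rate only at f = 0, and strict scoring only at f = 1.

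**Step 3: error rates, by what the 60% means.**

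- *The 60% excluded such responses, and all are due to the added agent (f = 1).* Under literal scoring the false-positive rate is 0.097 with no such patients, R(0.61) = 0.120 at +1 point, R(0.63) = 0.176 at +3 and R(0.65) = 0.247 at +5.
- *The 60% and 80% included them.* Literal scoring keeps 0.097. Strict scoring lowers power from 0.904 to R(0.78) = 0.847 if 2 points are such patients, and to R(0.75) = 0.730 if 5 points are.

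**The case against.** The claim rests on an omission. No sentence says that a response after salvage counts, and the objective suggests that the sponsor may intend otherwise. Response is a clinician's summary judgement, and the Appendix C forms, which might carry an instruction, are a separate document not available here. This stands as a limit: the point covers the text provided. It does not close the gap, because clinicians given no instruction could score the same patient differently and each be within the protocol.

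The affected group may be small. Prednisone increases are expressly not second-line therapy, and a patient who progressed must have no organ worse than before treatment by month 6. A patient already in PR before the added agent, or with a late study-drug effect, does not inflate ORR; section VI cites B-cell depletion lasting up to 48 weeks in the rheumatoid arthritis study. All of this stands, and is why f runs down to 0 above.

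Strict scoring could also break the match with the historical benchmark, since the Background says the metric was chosen with reference to published 6-month ORR. This stands too, and shapes the fix.

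A reader might go further and infer that the trial's false-positive rate is inflated. The documents do not support that. They do not say how the trials behind the 60% treated such patients. One is described as having a 6-month ORR and, separately, a treatment-failure endpoint that includes secondary treatment, which does not settle the question.

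**Conclusion.** The gap is real and should be fixed. The primary endpoint has no stated rule for a foreseeable event, and its literal reading conflicts with the objective and with the failure-free-survival definition. The size cannot be fixed from the documents. For an assumed 5 points of affected patients, the choice of scoring changes the verdict in 6.9% to 15.0% of trials at a regimen response of 60% and in 7.4% to 17.4% at 80%, depending on how many of the responses are due only to the added agent.

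The figure of 0.247 for the false-positive rate is an upper case. It needs 5 points, a benchmark that excluded such responses, and every one of them due to the added agent. With half due to it, the chance of rejecting at a regimen response of 60% is 0.160; with none, it stays at 0.097. Confidence is medium, because the response forms were not seen and the benchmark's scoring is unknown.

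**What to change.** In V.2.a, V.2.b and section VI, state before the analysis that a patient who starts a second-line systemic agent for progressive chronic GVHD before the 6-month assessment is a non-responder for ORR and CR, in both the 11-patient and 38-patient counts. Use the same trigger as the failure-free-survival event in V.2.g, with the V.2.e exclusions, so that the endpoints agree.

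Report the 6-month ORR regardless of second-line therapy beside it, and list for each affected patient whether CR or PR was recorded at a visit before the added agent.

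State how the trials behind the 60% scored such patients. If they counted them as responders, use the matching definition for the formal test against 60% and give the strict result as the sensitivity analysis.

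N and the boundaries stay the same. The cost is wording, one further analysis and one listing; immune suppressive medications are already recorded at the study visits where chronic GVHD is assessed. The downside is a slightly lower reported ORR, which undercounts patients already responding before the added agent, and the loss of power shown above if the strict rule is tested against a benchmark that included such responses.

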In the analysis of major published primary chronic GVHD therapy trials,¹⁵⁻²⁰ the following summarizes current evidence: Complete response rate assessed at 6-9 months following steroid based therapy (either 1mg/kg of prednisone alone or this in combination with additional agents such as azathioprine, thalidomide, hydroxychloroquine or mycophenolate mofetil) includes a range of reported values from 16% to 37%. In the study by *Sullivan, et al*, 9 month complete response rate to prednisone was 33%, prednisone + azathioprine 37%, and prednisone alone among high risk cases 16%.¹⁶ *Arora, et al* reported 6 month complete response rate of 17% in prednisone + thalidomide and cyclosporine, and 28% for prednisone and cyclosporine alone.¹⁷ In a more recent trial comparing activity of prednisone vs. prednisone and mycophenolate mofetil, *Martin, et al* reported a 6 month complete response rate of only 23%.¹⁹ Finally, *Gilman, et al* reported CR rates at 9 months of 38% and 33%, respectively for hydroxychloroquine + prednisone vs. prednisone alone. Thus, available randomized trials suggest an average complete response rate at 6-9 months of 27%. Overall response rate (ORR) (total of complete response (CR) + partial response (PR)) has been reported as the following: *Sullivan, et al* reported ORR of 62% among prednisone treated patients, 64% for prednisone with azathioprine, and only 32% for prednisone treated patients with thrombocytopenia.¹⁶ *Arora, et al* reported ORR of 84% at 6 months for prednisone treated patients and 88% for those treated with prednisone and thalidomide.¹⁷ *Martin, et al* reported an ORR of 62% at 6 months for patients treated with prednisone + mycophenolate mofetil or prednisone + placebo.^{19,21} *Gilman, et al* reported ORR at 9 months of 39% and 46% for hydroxychloroquine + prednisone vs. prednisone alone.¹⁸ Thus, published randomized trials support an average ORR at 6-9 months of 60%. Importantly, *Martin, et al* demonstrated that ORR at 6 months of therapy was significantly associated with the ultimate risk for treatment failure, defined as initiation of secondary systemic GVHD treatment, non-relapse death, or development of Bronchiolitis Obliterans. The cumulative incidence of treatment failure was 37% vs. 63% in those with overall response vs. not, $p = 0.01$.²¹

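### Failure-free survival has two event definitions that disagree on second-line agents started without progression

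*Combined protocol and SAP*

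**What the plan says.** Three places in the combined protocol and SAP bear on the FFS event.

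- **Section II, secondary objective 5** describes FFS as a "composite outcome of death, relapse and requirement for secondary immune suppressive agents". It gives no reason that the requirement must meet.
- **Section V.2.g** gives the composite as death from any cause, relapse and "addition of secondary immune suppressive agents for progressive chronic GVHD".
- **Section VI, Statistical Analysis plan** says that FFS will be estimated by Kaplan-Meier. It does not restate the event, and it does not say how an agent started without progression is handled.

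Two neighbouring items matter. Section V.2.e captures second-line systemic agents at each study visit with no general progression condition, but its item v counts newly started extracorporeal photopheresis (ECP) as second-line therapy when it is begun for progressive manifestations. Section IV.iii, on topical therapies, refers to endpoints that include a need for additional systemic therapy, again without a progression condition.

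**The concern.** One named endpoint has two event rules, and the patients on whom they differ are treatment failures in the ordinary sense: people whose disease did not respond well enough and who were given another systemic agent. An analyst who follows V.2.g leaves them failure-free at that point, and one who follows objective 5 counts them as failures.

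The choice affects how FFS can be used. The background (Assessment of therapeutic response in chronic GVHD) names FFS among the longer-term outcomes to which response measures are being related, and plans to study the association between response measures and long-term treatment success. Under V.2.g, a patient with stable disease who adds an agent is a non-responder for the primary endpoint yet failure-free, which blurs that association. If the definition is settled only after the data are seen, the choice can also be questioned as data-driven.

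**Working it through.** The documents state no FFS rate, power or margin, so there is no figure to reproduce. The check is a comparison of texts, followed by the effect of one discordant patient.

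**Step 1. What progressive means in this protocol.** The background section on response assessment sets out the clinician scale used for the primary endpoint: "SD indicates no response and no progression", and separately "PD indicates progressive chronic GVHD manifestations from baseline to response assessment". Non-response without worsening is therefore not progression on the protocol's own scale. A partial response that stays incomplete is not progression either.

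**Step 2. Apply both definitions to the possible courses.**

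| Course | Objective 5 | V.2.g |
|---|---|---|
| Death or relapse first | Event | Event, same date |
| Second agent started for progression | Event | Event, same date |
| Second agent started for stable disease or incomplete response, nothing further | Event at start | No event |
| As above, then death, relapse or an agent for progression | Event at first start | Event, later date |

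The definitions differ only in the last two rows. In both, V.2.g gives no event or a later one. For every patient the V.2.g event time is the same or later, so the underlying FFS probability is the same or higher at every time point.

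**Step 3. Effect per patient.** Take N = 38 (Section VI, Phase II component) and assume that all are followed to the time point. Kaplan-Meier then reduces to the proportion event-free. Let d be the number with an event under V.2.g, and k the number whose only event by that time is an agent started without progression.

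- FFS under V.2.g = (38 − d)/38
- FFS under objective 5 = (38 − d − k)/38
- Difference = k/38

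For k = 1 the difference is 1/38 = 2.6 percentage points. For assumed values of k = 2, 4 and 6 it is 5.3, 10.5 and 15.8 points. These values of k are illustrations only, as the documents give no expected count. A patient in the last row of the table stops contributing once the later event has occurred.

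**Step 4. Censoring.** With censoring, the contribution of one patient is no longer exactly 1/38, because a later event is weighed against a smaller risk set. The ordering of the estimates in Step 3 is therefore claimed only for complete follow-up.

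**The case against.** The best defence is that objective 5 is a short parenthetical summary and Section V is where endpoints are defined, so V.2.g elaborates the objective and does not contradict it. The same qualifier on ECP in V.2.e.v suggests that it was deliberate. This would carry weight if the document said that Section V governs, but it does not. The qualifier also does more than add detail, because it removes a class of patients that the objective's wording includes.

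Other parts of the defence stand, and they limit the point.

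- A reader might infer that V.2.g conflicts with the protocol's own definition of steroid-refractory disease, since the background describes it as "either progressive manifestations despite one month, or rather incomplete response despite two months of 1-2mg/kg of prednisone or equivalent". That passage reports common usage in the field. The operative statement, under exclusion criterion 2, describes refractory disease by progression and fits V.2.g. Likewise, the treatment-failure definition that counts initiation of secondary treatment whatever the reason belongs to a cited study. The point rests on the response scale and the two FFS texts alone.
- A reader might add steroid intolerance as a further reason that V.2.g misses. The documents do not mention it as a reason for a second agent.
- A reader might object that V.2.g depends on the open-label clinician's stated reason. Starting an agent is a clinician's decision under either text, the wider wording still needs attribution to chronic GVHD, and severity scores are recorded at scheduled visits. This is a minor consideration.
- Second-line utilisation and FFS are separate endpoints, so different counts would not in themselves be an error.

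**Conclusion.** The point holds as an unreconciled definition of a secondary endpoint. Objective 5 and V.2.g classify differently any patient who starts a second systemic agent for stable disease or incomplete response. With complete follow-up, V.2.g gives an equal or higher FFS.

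The size is 2.6 percentage points for each such patient with no other event. This assumes that FFS is reported on the 38 phase II patients and that none is censored before the time point. The total cannot be derived. A reader might put a figure on it: if 30% started a second agent and 25% to 50% of those starts were not for progression, the gap would be 0.30 × 0.25 = 7.5 to 0.30 × 0.50 = 15 points. Neither rate is in the documents, and the calculation treats every such patient as event-free for good, so it does not support a statement that FFS is overstated by that amount.

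Nor does the point reach the main result. FFS has no hypothesis test, threshold or power. The 6-month response decision, N = 38 and the toxicity stopping rule do not use it.

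**What to change.** - In V.2.g, delete the last four words of "addition of secondary immune suppressive agents for progressive chronic GVHD". State the event as death from any cause, relapse, or initiation of any second-line systemic agent for chronic GVHD, as captured in V.2.e, and use the same sentence in objective 5. The existing V.2.e exclusions (topical therapy, prednisone dose adjustment, and dose changes to existing agents to maintain drug levels) stay as they are.
- In V.2.e.v, remove the progression qualifier on ECP for endpoint counting. If V.2.g alone were changed, the same mismatch would remain for ECP.
- Record and tabulate the reason for each start. Sections V.3 and the study calendar provide for recording the agents but do not mention the reason. The Appendix C data forms are a separate document and may already hold it.
- If a progression-only version is wanted, report it as a labelled sensitivity analysis.

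These edits govern what is counted, not when any agent is given. The agents are already recorded at study visits, so the main FFS definition needs no new assessment. The cost is wording, possibly one field on the data form, and an FFS estimate that may be slightly less favourable. The change is best made before outcomes are analysed.
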